7.1.4. Administration of Study Medication

Administration of the study drug into the surgical site: A total of 10 mL (for Cohorts 1-4) and a total of 14 mL (for Cohort 5) of the investigative product will be administered into the surgical site as follows:

- At time of closure of capsule:
 - Infiltration of deep soft tissue and capsule with a total of:
 - 6 mL volume for Cohorts 1-4
 - 9 mL volume for Cohort 5
 - Instillation at cut bone with a total of 2 mL volume for all Cohorts
- Following closure of the capsule and prior to closure of the skin and subcutaneous layer:
 - Instillation of wound with 2 mL volume for Cohorts 1-4; study drug is applied to all exposed surfaces prior to subcutaneous and skin closure
 - Instillation of wound with 3 mL volume for Cohort 5; 2 mL of study drug will be instilled into the space under closed capsule, and 1 mL of study drug applied to all exposed surfaces prior to subcutaneous and skin closure)

7.1.5. Time 0 will be defined as the time of completion of drug administration. Day 1 (Post-Surgery) to Day 3 (Discharge)

Following surgery, subjects will be transferred to the appropriate recovery unit where they will undergo an assessment of safety and efficacy over the next 48 hours. The schedule of assessments are as follows:

- Pain intensity (assessed with NPRS): at 0.25, 0.5, 0.75, 1, 2, 4, 8, 12, 16, 20, 24, 28, 32, 36, 40, 44, and 48 hours after the administration of study medication. Assessments between the hours of 00:00 and 06:00 may be skipped if the subject is sleeping; however, consecutive assessments may not be skipped, and the Hour 12, Hour 24, and Hour 48 assessments must be completed even if the subject is asleep.
- Vital signs: 0.5, 1, 1.5, 2, 4, 6, 8, 10, 12, 16, 20, 24, 28, 32, 36, 40, 44, and 48 hours after the administration of study medication. Assessments between the hours of 00:00 and 06:00 may be skipped if the subject is sleeping; however, consecutive assessments may not be skipped, and the Hour 12, Hour 24, and Hour 48 assessments must be completed even if the subject is asleep.
- Physical exam: 1.0, 24, and 48 hours after the administration of study medication.
- ECG: 1.5 hours after the administration of study medication.
- Surgical Site assessment: 24 and 48 hours after the administration of study medication.
- Neurosensory Exam of the Foot / Great toe (bilateral): 24 and 48 hours after the administration of study medication.
- Clinical laboratory tests (chemistry/coagulation, hematology, and urinalysis): 1.5 hours after the administration of study medication.
- Blood draw for PK analysis: are at baseline (before dosing), and at 5 minutes, 15 minutes, 30 minutes, 45 minutes, and 1, 1.5, 2, 2.5, 3, 3.5, 4, 6, 8, 12, 16, 24, 36, and 48 hours after dosing.
- Subjects with inadequately controlled pain may request rescue at any time; however, subjects will be encouraged to receive rescue medication only with an NPRS ≥ 4 . Additionally, subjects should be encouraged to wait at least 1 hour after completion of surgery (i.e. completion of sutures) before utilizing pain rescue medication, if possible. Pain intensity (NPRS) will also be completed within 15 minutes prior to use of pain rescue medication.
- Concomitant medications.
- All SAEs that occur from the time a subject's informed consent will be captured. All SAEs and non-serious AEs will be documented and followed from the time of administration of study drug. Non-serious AEs that occur between Screening and the study procedure should be considered medical history, and be added to the subject's medical record.

After completing the assessments through 48 hours after study medication administration, the diary for at-home use will be reviewed and subjects will be discharged from the study center with

diary to record pain assessments and pain medication at home. Subjects will be provided routine standard of care for pain management after discharge from the study center. Subjects will be instructed to return to the study center on Day 8 [± 1 day] for follow-up assessments.

7.1.6. Days 3 through 8:

In their diary, subjects will assess their pain intensity once in the morning (08:00 ± 4 hours), and once in the evening (20:00 ± 4 hours) using the NPRS. Subjects will also record any medication they take to treat their pain, and will capture an additional NPRS within 15 minutes prior to each dose of pain medication.

Subjects will return to the study center on Day 8 [± 1 day] for the following assessments:

- Subject home diary review (pain intensity and pain medication)
- Pain Intensity (NPRS)
- Vital signs
- Surgical Site assessment
- Neurosensory Exam of the Foot / Great toe (bilateral)
- Concomitant Medication Use
- AE Assessment
- Brief Pain Inventory-Short Form (BPI-SF)
- Patient Global Evaluation (PGE)
- Investigator Global Evaluation (IGE)

7.1.7. Days 9 through 15:

In their take-home Diary, subjects will assess their pain intensity once in the morning (08:00 ± 4 hours), and once in the evening (20:00 ± 4 hours) using the NPRS. Subjects will also record any medication they take to treat their pain.

Subjects will return to the study center on Day 15 [± 2 days] for the following assessments:

- Subject home diary review (pain intensity and pain medication)
- Pain Intensity (NPRS)
- BPI-SF
- PGE
- IGE
- Vital signs
- Surgical Site assessment
- Neurosensory Exam of the Foot / Great toe (bilateral)
- Concomitant Medication Use
- AE Assessment

7.1.8. Day 29 / Early Termination

Subjects will return to the study center on Day 29 [± 2 days], or at the time of discontinuation, for the following assessments:

- Subject home diary review (pain intensity and pain medication, *if* ET is \leq Day 15)
- Pain Intensity (NPRS)
- BPI-SF
- PGE
- IGE
- PE
- Vital signs
- X-ray of Surgical Site
- Surgical Site assessment (when assessed, if the Investigator observes insufficient wound healing, the subject will be scheduled for a follow-up visit on Day 36. If the wound is considered healed at Day 29, Day 36 is not required.)
- Neurosensory Exam of the Foot / Great toe (bilateral)

- Concomitant Medication Use
- AE Assessment

7.1.9. Day 36 (if required)

If required due to insufficient wound healing noted at Day 29 visit, Subjects will return to the study center on Day 36 [± 2 days] for the following assessments:

- Surgical Site assessment
- Neurosensory Exam of the Foot / Great toe (bilateral)
- Concomitant Medication Use
- AE Assessment

7.1.10. Unscheduled Visit

Assessments performed at Unscheduled Visits will be at the discretion of the Investigator.

7.2. Discussion of Study Design

This trial is designed to determine the recommended dose and define the toxicity profile of CA-008.

The current design, post-operative pain following elective primary unilateral first metatarsal bunionectomy surgery with osteotomy, has been used as a model of postoperative pain previously. In this model, the pain is generated from the correction of hallux valgus deformities of the first metatarsal and is used as a model to assess adequate duration of acute pain to measure multiple-day efficacy ([Singla et al., 2013](#); [Wang et al., 2010](#)).

Randomization will be used to avoid bias in the assignment of subjects to treatment, to increase the likelihood that known and unknown subject attributes (e.g., demographics and baseline characteristics) are evenly balanced across treatment groups, and to enhance the validity of statistical comparisons across treatment groups.

A placebo control will be used to establish the frequency and magnitude of changes in clinical endpoints that may occur in the absence of active treatment as well as to minimize subject and investigator bias. Double-blinded treatments will be used to reduce potential bias of subjects and investigators during data collection and evaluation of clinical endpoints.

8. SELECTION OF STUDY POPULATION

8.1. Inclusion Criteria

Subjects must meet all of the following criteria to be considered eligible to participate in the study:

1. Male or female aged 18 - 65 years old, inclusive.
2. Planning to undergo a primary unilateral first metatarsal bunionectomy repair, without collateral procedures.
3. Be American Society of Anesthesiology (ASA) physical Class 1 or 2. [Appendix J](#)
4. In good health and capable of undergoing a bunionectomy under regional anesthesia.
5. No additional planned surgeries other than a bunionectomy during the course of the study.
6. Male subjects must be either sterile (surgically or biologically), or commit to an acceptable method of birth control while participating in the study.
7. Female subjects are eligible only if all of the following apply:
 - a. Not pregnant (female subject of child bearing potential must have a negative serum pregnancy tests at screening and negative urine pregnancy test before surgery);
 - b. Not lactating;
 - c. Not planning to become pregnant during the study;
 - d. Be surgically sterile; or at least two years post-menopausal; or have a monogamous partner who is surgically sterile; or is practicing double-barrier contraception; or practicing abstinence (must agree to use double-barrier contraception in the event of sexual activity); or using an insertable, injectable, transdermal, or combination oral contraceptive approved by the FDA for greater than 2 months prior to screening visits and commits to the use of an acceptable form of birth control for the duration of the study and for 30 days from completion of the study.
8. Have a body mass index $\leq 35 \text{ kg/m}^2$.
9. Willing and able to sign the informed consent form (ICF) approved by the Institutional Review Board (IRB).
10. Willing and able to complete the study procedures and pain scales, and to communicate meaningfully in English with study personnel.

8.2. Exclusion Criteria

Subjects will not be eligible to participate in this study if any one of the following exclusion criteria is met:

1. Subjects with a history of hypertension, cardiovascular disease or a history of cerebrovascular events.
2. Subjects with concurrent painful conditions that may require analgesic treatment during the study period, or, in the opinion of the Investigator, may confound post-operative pain assessments.
3. Have been receiving or have received chronic opioid therapy defined as greater than 15 morphine equivalents units per day for greater than 3 out of 7 days per week over a one-month period within 12 months of study treatment initiation.
4. Have a known allergy or intolerance to the following medications or related substances: capsaicin, chili peppers, propofol, bupivacaine, benzodiazepines, midazolam, oxycodone, fentanyl or ondansetron.

5. Have a clinically significant abnormal clinical laboratory test value that places the subject at undue risk according to the judgment of the investigator.
6. Have, as determined by the investigator or the study's medical monitor, a history or clinical manifestations of significant renal, hepatic, cardiovascular, metabolic, neurologic, psychiatric, or other condition that would preclude participation in the study.
7. Use concurrent therapy that could interfere with the evaluation of efficacy or safety, such as any drugs which, in the investigator's opinion, may exert significant analgesic properties or act synergistically with CA-008.
8. Use of disallowed pain medications within 2 days prior to Day 1 (NSAIDs, COX-2 inhibitors, tramadol, ketamine, clonidine, gabapentin, pregabalin, or cannabinoids).
9. Use of central nervous system (CNS) active drugs such as benzodiazepines, tricyclic antidepressants, SNRIs, or SSRIs for pain within seven days prior to Day 1. These drugs are permitted for non-pain indications if the dose has been stable for at least 30 days prior to Day 1 and is planned to remain stable throughout the study. The use of lorazepam and other sleep medications, except those containing analgesic properties, is permitted.
10. Have evidence of a clinically significant 12-lead ECG abnormality according to the judgment of the investigator, including QTcF >450 for men and >470 for women.
11. Use of dietary supplements or over-the-counter (OTC) medications containing significant amounts of capsaicin within 1 day prior to Day 1, and throughout the hospitalization period.
12. Subjects with active cutaneous disease, or other disease, at the anticipated site of surgery.
13. History of peripheral vascular disease, sickle cell disease, vascular grafts, or vasospastic disorders.
14. Use of parenteral or oral corticosteroid(s) within 14 days prior to Day 1.
15. Known bleeding disorder or is taking agents affecting coagulation preoperatively. Deep venous thrombosis (DVT) prophylaxis of the surgeon's choice is permitted postoperatively.
16. A medical condition that in the investigator's opinion could adversely impact the subject's participation or safety, conduct of the study, or interfere with the pain assessments.
17. Diabetes mellitus.
18. Use of antihypertensive agent or diabetic regimen at a dose that has not been stable for at least 30 days, or which is not expected to remain stable throughout the study.
19. Use of digoxin, warfarin (see exception below), lithium, theophylline preparations, aminoglycosides, and all antiarrhythmics except beta-blockers, and use of anticonvulsants except benzodiazepines within 7 days prior to Day 1 and throughout the study. (Use of warfarin is allowed, at the investigator's discretion, for DVT prophylaxis after the surgery).
20. History of illicit drug use, or prescription medicine or alcohol abuse (regularly drinks > 4 units of alcohol per day; 8 oz. beer, 3 oz. wine, 1 oz. spirits) within the past 2 years, in the opinion of the Investigator.
21. Have positive results on the alcohol breath test indicative of alcohol abuse or urine drug screen indicative of illicit drug use (unless results can be explained by a current prescription or acceptable over-the-counter medication at screening as determined by the investigator) at screening, and/or prior to surgery.
22. Participated in another clinical trial or used an investigational product within 30 days or five half-lives (whichever is longer) prior to the planned bunionectomy surgery, or is scheduled to receive an investigational product other than CA-008 while participating in the study.
23. Previously participated in a clinical study with CA-008 or capsaicin.
24. Subjects with peripheral neuropathies which would potentially confound the planned neurosensory testing.
25. Subjects who donated blood or plasma within the 30 days prior to screening.

8.3. Removal of Subjects from Therapy or Assessment

A subject is free to withdraw his/her consent and discontinue participation in the study at any time for any reason. A subject's participation must therefore be terminated immediately upon his/her request, and the reason(s) for discontinuation appropriately documented.

A subject may be discontinued from the study for any of the following reasons:

- Safety reasons, including AEs or significant concomitant illness, injury, or urgent surgeries/procedures that would, in the judgment of the Investigator, affect assessments of clinical status to a significant extent, require discontinuation of study drug, or both
- At the request of the Sponsor, regulatory agency, or Institutional Review Board (IRB)
- Subject is lost to follow-up
- Subject treatment allocation is unblinded (i.e., individual code break; Section 9.6)
- Death of subject

A subject may also be discontinued from the study, at the discretion of the Investigator and/or Sponsor, for any of the following reasons:

- Subject refuses or is unable to adhere to the study protocol
- Major protocol violation
- Pregnancy
- Use of unacceptable concomitant medication(s)
- It is not considered in the best interest of the subject to continue
- Administrative reasons (e.g., termination of enrollment or study)

The Investigator must maintain a record of all subjects who discontinue from the study prior to completion; the reason(s) for study discontinuation will be documented. In the event that a subject chooses to withdraw from the study, the Investigator should make a reasonable attempt to obtain and record the reason(s) for withdrawal in as much detail as possible, although the subject is not obligated to provide such a reason.

In the event that a subject is discontinued while at the clinical site, the early termination procedures shown in the Schedule of Assessments (Table 1) should be performed prior to discharge from the clinical site. The Investigator should ask the subject to for the Follow-up procedures, provided that the subject has not withdrawn consent for those procedures. If a subject refuses to complete early termination/Follow-up procedures or continued data collection, this information will be recorded.

8.4. Study Stopping Rules

Dose escalation, or continuation of dosing, will not occur if subjects in a cohort experience intolerable treatment related AEs on active drug, as defined below:

- 1 or more treatment-related AE of grade 4 or higher (per Table 2, Appendix G, or Appendix H);
- 2 or more treatment-related AEs of grade 3 or higher (per Table 2, Appendix G, or Appendix H)

Table 2 Study Stopping Rules

Category	Mild (Grade 1)	Moderate (Grade 2)	Severe (Grade 3)	Potentially Life Threatening (Grade 4)
Abnormal Wound Healing: Infection Dehiscence Necrosis	Mild symptoms; clinical or diagnostic observations only; intervention not indicated. No interference with age- appropriate instrumental ADL	Minimal, local or noninvasive intervention indicated; May require local wound care or medical intervention (e.g., dressings or topical medications)	Severe or medically significant but not immediately life- threatening; hospitalization or prolongation of existing hospitalization indicated; limiting ADLs. May require IV antibiotics, antifungals, or antivirals or radiologic intervention.	Life-threatening consequences; urgent intervention indicated
ECG/Cardiac issues Vital Signs Labs	Asymptomatic, intervention not indicated	Non-urgent medical intervention indicated	Severe or medically significant but not immediately life- threatening; hospitalization or prolongation of existing hospitalization indicated	Life-threatening consequences; urgent intervention indicated
Focused Neurosensory Testing (performed by trained Investigator)	Mild symptoms	Moderate symptoms; limiting instrumental ADL	Severe symptoms requiring medical intervention; limiting self-care ADL	Life-threatening and urgent intervention indicated

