	use of the rescue therapy/medication will be collected through Day 15 or early termination (by site staff during the inpatient stay, and via Subject Diary during the outpatient portion).
AE Considerations:	
The following is a partial list of additional AE considerations for the protocol, based on FDA comments:
 
 • Vital signs-based adverse event definitions will be pre-specified in the protocol. • Any sensory deficits or clinically significant persistent sensory change at time of discharge, such as allodynia or hyperalgesia must be designated as a neurologic AE. Subjects will be followed until there is full return to baseline for the neurosensory assessment or until there is a determination that it is most likely going to be a permanent change and, consequently, classified as an adverse event. • Numbness at or near the incision need not be considered a neurologic AE since this could occur as a result of tissue trauma and inflammation from the surgery. • If a subject develops cardiac adverse events (chest pain, change in heart rate, shortness of breath or diaphoresis) a 12-lead ECG must be performed and read by a qualified physician.
Study Stopping Rules:	
Dose escalation, or continuation of dosing, will not occur if subjects in a cohort experience intolerable treatment related AEs on active drug, as defined below:
 
 • 1 or more treatment-related AE of grade 4 or higher (per Table 2, Appendix G or Appendix H); • 2 or more treatment-related AEs of grade 3 or higher (per Table 2, Appendix G or Appendix H)
Sample Size Justification:	Sample size is appropriate for Phase 1 dose ranging safety study.
Data Analysis Plan:	
Two analysis populations will be defined as follows:
 
 • Safety Population will include all subjects who received at least one dose of study drug. • PK Population: will include all subjects who received a full dose of study drug and have sufficient concentration-time profiles for estimation of PK parameters. 
All safety assessments and baseline characteristics will be summarized using the Safety Population. PK analyses will be performed using the PK population. All summaries will be grouped by the actual treatment received. Placebo subjects will be combined for summaries.

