	
Safety and tolerability will be evaluated by examining the occurrence of AEs, including Treatment-Emergent AEs. AEs leading to discontinuation from the study, AEs related to the study dose, and AE severity will be summarized by treatment group.
 
Actual and change from baseline in clinical laboratory measures, vital signs, and ECGs will also be assessed and summarized by treatment group. These data will be summarized using descriptive statistics including n, mean, SD, SEM (if appropriate), median, minimum and maximum. Abnormal values will be determined and flagged in the listings. Laboratory shift tables displaying the change (number of subjects) relative to the normal range from baseline to each study visit will also be presented by treatment for each test. The Investigator should exercise medical and scientific judgment in deciding whether an abnormal laboratory finding or other abnormal assessment is clinically significant.
 
The study is not designed to detect a significant difference in analgesia between the two treatment groups. All secondary efficacy endpoints (e.g., NPRS scores), will be summarized over time by treatment using descriptive statistics including confidence intervals as appropriate.

Data Monitoring Committee (DMC):	Safety data will be reviewed by a DMC after the final dosing within each cohort to determine appropriate dose escalation in the next planned cohort.

Table 1 Schedule of Assessments

Assessment	Screening	In Patient					Discharge through EOS	Follow-Up			ET ²
		Prior to Surgery	Surgery	Post-Surgery	24 hr	48 hr		8 ±1 day	15 ±2 days	29 ±2 days	
Study Day	-28 to -1	1	1	1	2	3					
Informed Consent	X										
Screening Medical and Surgical History	X	X									
Inclusion/Exclusion Criteria	X	X									
Screens for alcohol/drugs of abuse	X	X									
Enroll/Randomize		X									
Demographics	X										
Subject Pain Assessment Training	X	X									
Surgery			X								
Infiltration			X								
Safety Evaluations											
Pregnancy Test	X (serum)	X ³ (urine)									
Vital Signs	X	X		X ⁴	X ⁴	X ⁴		X	X	X	X
Physical Exam ⁵	X ⁵	X ⁵		X ⁵	X ⁵	X ⁵				X ⁵	X
12-Lead ECG	X			X ⁶							
Surgical Site assessment	X	X			X ⁷	X ⁷		X	X	X	X
Neurosensory Exam	X	X			X ⁸	X ⁸		X	X	X	X
Blood draw for hematology and serum chemistry/coagulation	X	X		X ⁹							
Urine sample for urinalysis	X	X		X ⁹							
X-ray of Surgical Site	X								X		X
Concomitant Medication Assessment	X	X		X	X	X		X	X	X	X
Adverse Event Assessment	X	X	X	X	X	X		X	X	X	X

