10.5.7. Surgical Site Assessment

Surgical Sites should be assessed to determine if any site related AEs have occurred. Assessments will be conducted at screening, baseline and then at 24 hours (± 2 hours) and 48 hours (± 4 hours) after the administration of study medication. During the first 48 hours, the investigator will evaluate their satisfaction with the healing of the wound during this Surgical Site assessment using an 11-point scale (0-10) where a score of 0 is "Completely unsatisfied," and a score of 10 is "Completely satisfied." [Appendix C](#)

Assessments will also be performed at each of the Follow-up visits on Days 8, 15 and 29, or at the time of discontinuation. When assessed on Day 29, if the Investigator observes insufficient wound healing, the subject will be scheduled for a follow-up visit on Day 36. [Appendix I](#)

If there are skin reactions, for example, erythema, pain, pruritus, bruising, swelling, bruising or other skin changes, they will be evaluated and graded for severity regularly until resolution.

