13.4.9. Physical Examination Findings

Physical and Surgical Site examination data will be presented in the listings. Abnormal or clinically significant physical exam and surgical site findings will be recorded as AEs.

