APPENDIX F: INVESTIGATOR GLOBAL EVALUATION (IGE)

Investigator Global Evaluation (IGE)

Instructions to Investigator: Please respond to the question below. When completed, please initial at the bottom of the page.

How would you rate the study medication that this patient received for pain?

(Mark one box)

Excellent (3)

Good (2)

Fair (1)

Poor (0)

Investigator Initials: _____

APPENDIX G: GUIDANCE FOR INDUSTRY: TOXICITY GRADING SCALE FOR HEALTHY ADULT AND ADOLESCENT VOLUNTEERS ENROLLED IN PREVENTIVE VACCINE CLINICAL TRIALS, TABLE FOR CLINICAL VITAL SIGN ABNORMALITIES

Vital Signs *	Mild (Grade 1)	Moderate (Grade 2)	Severe (Grade 3)	Potentially Life Threatening (Grade 4)
Fever (°C) ** (°F) *	38.0 – 38.4 100.4 – 101.1	38.5 – 38.9 101.2 – 102.0	39.0 – 40 102.1 – 104	> 40 > 104
Tachycardia - beats per minute	101 – 115	116 – 130	> 130	ER visit or hospitalization for arrhythmia
Bradycardia - beats per minute***	50 – 54	45 – 49	< 45	ER visit or hospitalization for arrhythmia
Hypertension (systolic) - mm Hg	141 – 150	151 – 155	> 155	ER visit or hospitalization for malignant hypertension
Hypertension (diastolic) - mm Hg	91 – 95	96 – 100	> 100	ER visit or hospitalization for malignant hypertension
Hypotension (systolic) – mm Hg	85 – 89	80 – 84	< 80	ER visit or hospitalization for hypotensive shock
Respiratory Rate – breaths per minute	17 – 20	21 – 25	> 25	Intubation

* Subject should be at rest for all vital sign measurements.

** Oral temperature; no recent hot or cold beverages or smoking.

*** When resting heart rate is between 60 - 100 beats per minute. Use clinical judgement when characterizing bradycardia among some healthy subject populations, for example, conditioned athletes.

APPENDIX H: GUIDANCE FOR INDUSTRY: TOXICITY GRADING SCALE FOR HEALTHY ADULT AND ADOLESCENT VOLUNTEERS ENROLLED IN PREVENTIVE VACCINE CLINICAL TRIALS, TABLE FOR LABORATORY ABNORMALITIES

Serum *	Mild (Grade 1)	Moderate (Grade 2)	Severe (Grade 3)	Potentially Life Threatening (Grade 4)**
Sodium – Hyponatremia mEq/L	132 – 134	130 – 131	125 – 129	< 125
Sodium – Hypernatremia mEq/L	144 – 145	146 – 147	148 – 150	> 150
Potassium – Hyperkalemia mEq/L	5.1 – 5.2	5.3 – 5.4	5.5 – 5.6	> 5.6
Potassium – Hypokalemia mEq/L	3.5 – 3.6	3.3 – 3.4	3.1 – 3.2	< 3.1
Glucose – Hypoglycemia mg/dL	65 – 69	55 – 64	45 – 54	< 45
Glucose – Hyperglycemia				Insulin requirements or hyperosmolar coma
Fasting – mg/dL	100 – 110	111 – 125	>125	
Random – mg/dL	110 – 125	126 – 200	>200	

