11 INTERIM ANALYSES AND DATA MONITORING

There are no planned interim analyses for this study.

A DMC will regularly monitor safety data in a blinded fashion throughout the study. To determine appropriate dose escalation in the next planned cohort, safety data will be reviewed by a DMC after the final dosing within each cohort. Details regarding the DMC are included in the DMC Charter.

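### The stopping rule counts only related AEs that Table 2, Appendix G or Appendix H can grade; other severe related AEs add nothing to the count and are left to discretion

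*Protocol*

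**What the plan says.** Protocol 8.4 bars escalation, or continued dosing, when subjects in a cohort have intolerable related AEs on active drug. Two bullets define intolerable: one related AE of Grade 4 or higher, or "2 or more treatment-related AEs of grade 3 or higher (per Table 2, Appendix G, or Appendix H"). The synopsis repeats the rule: "2 or more treatment-related AEs of grade 3 or higher (per Table 2, Appendix G or Appendix H"). SAP 2.2 refers back to the protocol and adds no definition.

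The grading sources contain the following:

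- **Table 2** has three rows: abnormal wound healing, naming infection, dehiscence and necrosis; ECG/cardiac issues, vital signs and labs; and focused neurosensory testing.
- **Appendix G** grades vital signs. Its Grade 4 column includes entries such as "ER visit or hospitalization for hypotensive shock".
- **Appendix H** grades serum laboratory values.

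Elsewhere the protocol expects AEs of other kinds. Section 10.5.7 states: "Surgical Sites should be assessed to determine if any site related AEs have occurred". It also mentions skin reactions such as erythema, bruising and swelling. Section 13.4.9 states: "Abnormal or clinically significant physical exam and surgical site findings will be recorded as AEs". Appendix I scores erythema, drainage, edema, induration and hematoma from 0 to 4, but the rule does not cite it.

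On oversight, the synopsis says: "Safety data will be reviewed by a DMC after the final dosing within each cohort". SAP 11 agrees: "safety data will be reviewed by a DMC after the final dosing within each cohort".

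**The concern.** A rule that counts AEs of Grade 3 or higher can count only what has a grade. The protocol collects surgical-site findings as AEs, and its background (5.1.2) names erythema among the immediate effects of TRPV1 activation. Yet none of the three grading sources has a row for a local reaction that is neither neurosensory nor abnormal wound healing. Nor is there a row for any other clinical AE without a cardiac, vital-sign, laboratory or neurosensory component.

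The gap exists in every cohort, but it can now matter only in Cohort 5. The study rationale (5.2) says that the first four cohorts have been studied, and the Amendment 2 text expects no escalation beyond Cohort 5. What remains for the rule is to decide whether dosing continues within that cohort: six active subjects at 4.2 mg, without sentinel dosing, and with the scheduled DMC review placed after the last subject is dosed.

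**Working it through.** **Plan's own figure.** There is none to reproduce. The documents give no operating characteristics for the rule and no event rates, and SAP 2.2.4 says that the sample size has no statistical basis.

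**Step 1: which related AEs have a grade.**

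| Related AE | Source of grade | Counts? |
|---|---|---|
| Wound infection, dehiscence, necrosis | Table 2, row 1 | Yes |
| Cardiac, vital-sign or laboratory event | Table 2, row 2; Appendices G and H | Yes |
| Allodynia, hyperalgesia (arguably burning) | Table 2, row 3 | Yes |
| Erythema with eschar | Arguably necrosis, row 1 | Arguably |
| Edema, hematoma or erythema not classed as abnormal wound healing | None | No |
| Other clinical AE with none of the above components | None | No |

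**Step 2: effect on the count, with no rate assumed.** The fix adds a catch-all row whose Grade 3 requires hospitalization or its prolongation to be indicated, or self-care to be limited (the anchor).

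| Events in the cohort | Count now | Count after fix |
|---|---|---|
| Two uncovered AEs, both meeting the anchor | 0 | 2 (stop) |
| One covered Grade 3 AE and one uncovered AE meeting the anchor | 1 | 2 (stop) |
| Two uncovered severe AEs, neither meeting the anchor | 0 | 0 |

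**Step 3: illustration with assumed rates.** Let n = 6 active subjects (Protocol 7.1). Let q be the per-subject rate of covered Grade 3 related AEs, and u the rate of uncovered related AEs that meet the anchor. Take X ~ Bin(n, q) and Y ~ Bin(n, u), independent, with at most one event of each type per subject. Grade 4 events are left out. Then

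added chance of a stop = P(X + Y ≥ 2) − P(X ≥ 2).

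- u = 5%, q = 0: 1 − 0.95^6 − 6(0.05)(0.95^5) = 1 − 0.7351 − 0.2321 = 0.0328, or 3.3 points.
- If 5% is the rate of all uncovered severe AEs and half meet the anchor (an assumption), u = 2.5%: 1 − 0.8591 − 0.1322 = 0.0088 before rounding of the terms, or 0.9 points.
- u = q = 5%: 0.1184 − 0.0328 = 0.0856, or 8.6 points.

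Added chance in percentage points, n = 6:

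| | u = 2.5% | u = 5% | u = 10% |
|---|---|---|---|
| q = 0 | 0.9 | 3.3 | 11.4 |
| q = 5% | 3.9 | 8.6 | 19.3 |
| q = 10% | 5.5 | 11.1 | 22.7 |

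**Step 4: blinded review.** Cohort reviews are blinded (Protocol 8.5 and 9.6). If placebo events were counted too, at the same rates, n = 8 and u = q = 5% give 0.1892 − 0.0572 = 0.1320, or 13.2 points.

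**Step 5: subjects spared by a stop.** At most 5 of the 6 active subjects, if both AEs occur in the first one dosed; 0 if all are dosed before the AEs are known. The protocol does not give the dosing spacing within Cohort 5, and scheduled site assessments start at 24 hours (7.1.5).

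**The case against.** The strongest reply is that a short list of hard triggers backed by committee judgement is a legitimate Phase 1 design. The DMC monitors all aspects of safety throughout, and surgical-site assessments and TEAEs are among the data it may use (8.5). The sponsor may suspend the study at any time (14.3). An event that requires hospitalization is already an SAE, reportable within 24 hours (11.1.3 and 11.1.3.1). The DMC Charter, which is not among the documents, may say more. All of this stands as a backstop. It does not change the count under 8.4, and a prespecified rule exists so that a stop need not depend on discretion.

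Second, the three terms in the wound row could be examples under a broader heading. An edema or hematoma serious enough to indicate hospitalization might then be graded there. The text neither says this nor rules it out. A non-wound clinical AE would still have no row.

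Third, Cohort 5 raises volume from 10 to 14 mL at an unchanged 300 µg/mL, and section 5.2 reports no safety or tolerability concerns in Cohorts 1–4. That is not a zero event rate, but it argues against the higher assumed values of u.

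A reader might infer that no severe local reaction short of infection, dehiscence or necrosis can count, or that nothing could halt Cohort 5 after such reactions. The documents do not support either. Allodynia and hyperalgesia are graded in Table 2, vital-sign and laboratory consequences count, most life-threatening events are covered, and the DMC and sponsor can act.

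**Conclusion.** The gap is real and limited. Followed as written, the rule gives no count to related AEs outside its graded categories, in any cohort, and leaves them to DMC or sponsor judgement. Only continuation of dosing in Cohort 5 can still be affected.

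The firm result needs no rate: two uncovered related AEs that meet the proposed Grade 3 anchor count 0 now and would count 2 with the fix. It would be tempting to read the probabilities as the effect for all severe uncovered AEs. They hold only when u is the anchor-meeting rate; if u is taken as the rate of all severe uncovered AEs, they are ceilings. All rates are assumptions, as are independence and at most one event of each type per subject. The change should be made. The discretionary safeguards keep it from being a critical fault.

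**What to change.** Add a fourth row to Table 2, *Any other treatment-related AE*, using descriptors already in the table:

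- **Grade 3:** the descriptor of the ECG/vital signs/labs row, which includes "hospitalization or prolongation of existing hospitalization indicated"; or, as an alternative criterion, the self-care limitation from the neurosensory row.
- **Grade 4:** the life-threatening, urgent-intervention descriptor of the existing rows.

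Both bullets, in 8.4 and the synopsis, already cite Table 2, so nothing else in the rule needs rewording. Do not use the severity labels in 11.1.2 as grades, because they have no definitions. Do not use Appendix I scores, NPRS scores or rescue use, which could turn ordinary postoperative swelling or pain into triggers. Check the DMC Charter for consistency.

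The cost is one table row and no new data collection, but it is a protocol amendment that needs IRB approval before use (14.6). The rule may be met somewhat more often, with possibly some false stops; their number cannot be estimated because the documents give no event rate. The hospitalization and self-care anchors limit them.
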